## **9.4 DATA SOURCES**

Two large US claims databases (Truven Marketscan Commercial Claims and Encounters (CCAE), Truven Marketscan Medicare Supplemental (MDCR), and Optum Clininformatics® Data Mart [CDM]) will be used in this study. Meta-analysis of the 2 databases might be used, when appropriate, to achieve the required study size.

Main data elements from each database that will be used in this analysis include: 1) enrolment records, 2) pharmacy dispensing claims (dispensing date, National Drug Code [NDC] to determine product prescribed, quantity, and days of supply, and 3) medical claims (service date, diagnosis codes [ICD-9-CM, ICD-10-CM], procedure codes [Current Procedural Terminology (CPT)-4, ICD-9 Procedure Coding System (PCS), ICD-10-PCS], and laboratory test results (when available).

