## **9.5 STUDY SIZE**

All patients with T2DM who newly initiate therapy with empagliflozin or study comparator who meet the inclusion and exclusion criteria will be included in the analysis.

Event rate of acute pancreatitis reported in patients with T2DM who are treated with canagliflozin was reported to be 2.2 per 1000 PY [\[RRA-21430\]](#). This rate was used for sample size calculation using the formula of Farrington and Manning (maximum likelihood method) [\[R14-3295\]](#).

Null hypothesis H0:  $\pi_2 / \pi_1 \geq 1.5$  (non-inferiority)

A single stage (fixed sample size) design was chosen.

For specified  $\alpha = 0.05$  and rates  $\pi_1 = 0.0022$  and  $\pi_2 = 0.0022$  (odds ratio of 1.000) the power (1 -  $\beta$ ) is 80.0% if the test stages consist of the sample sizes given in the last two columns of [Table 1](#).

The computation assumes an allocation ratio (n2/n1) = 1 (Table 1). It is assumed that all patients have 1 year of follow up.

**Table 1** Number of empagliflozin initiators and empagliflozin-exposed person-years needed to detect a HR of 1.5 and 2.0 with a power of 80% and  $\alpha = 0.05$  under 1:1 matching ratio

Hazard ratio (HR)	Information rate	Bunds accept $H_0$	Bunds reject $H_0$	sign.level one-sided	$\alpha$ spent	$\beta$ spent	power achieved	Observations per exposure group	Overall observations
1.5	1.0	1.645	1.645	0.0500	0.0500	-	0.8000	34585.4	69170.8

ADDPLAN Adaptive Design Software 2019 and SAS 9.4 software ( ) were used to calculate the sample size.

Analysis of this study will be initiated as soon as a sufficient sample size to exclude a HR of 1.5 with 80% power is reached. Based on a feasibility assessment conducted in Optum and MarketScan databases using data between 1 August 2014 and the latest data-cut available in MarketScan (30 September 2020) and Optum (31 March 2021), the dual-therapy cohort was reported with the highest number of empagliflozin initiators, therefore meta-analysis of the dual therapy cohorts including the data from the MarketScan and Optum databases will be the main analysis of this study as it will be the only powered analysis.

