### **9.9.1 Data source**

The source claims data include limitations with respect to certainty of the capture of exposure, covariates, and outcomes. As a comprehensive insurance database, essentially all billable medical services will result in claims for reimbursement, so that the certainty of capture is tied to likelihood of a claim being submitted to the insurer.

Although duration of diabetes may represent a risk factor for the study outcome, this covariate will be incompletely captured since the patient history in the dataset is relatively short (at least 12 months, and an average of approximately 2 years), and a first claim within the database may not represent diabetes onset since the condition can be latent for some time and is typically not treated with hypoglycaemic medications at its diagnosis.

New initiators are operationally defined as patients with no use in the prior 6 months. This does not ensure, however, that patients have never used the drug of interest; the possibility remains that these patients were treated at some prior time point before they enrolled in their insurance plan.

There is potential for misclassification of dose based on healthcare utilization data, but the “days supply” field is expected to be fairly accurate. Similar concern may be present for exposure classification as well, but we expect the drug codes utilized in the data sources will appropriately represent the drug that is being classified.

Medication use in administrative healthcare databases is restricted to prescription drug medication. Consequently, the use of over-the counter (OTC) medications (e.g., OTC aspirin) is not captured. Additionally, the indication of a claim for prescription medications does not confirm whether the medication was actually taken by the patient or taken as prescribed.

It is estimated that two databases (MarketScan and Optum CDM) have about 10-15% overlap and it is not possible to identify duplicates and remove them between the two databases because patients are de-identified. It is not expected that this overlap impacts the results of this study because it will be much smaller in the study population. Furthermore, there is a sensitivity analysis to consider several scenarios of overlap in patients between the MarketScan and Optum (e.g., 0%, 10%, 20%, etc.), and 95% CIs of primary outcome will be adjusted accordingly.

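### Section 9.5 sizes the only powered analysis on independent observations, yet the count is to be filled from two overlapping databases: power at 34,585 per group is below 80% by an amount the plan does not state, and no overlap value is named for the main confidence interval

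*Protocol*

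**What the plan says.** Protocol 9.5 (Study size) uses the Farrington-Manning formula with a rate of 0.0022 in both groups, taken from a report that the rate in patients "treated with canagliflozin was reported to be 2.2 per 1000 PY". The margin is a ratio of 1.5, allocation is 1:1, and every patient is assumed to have one year of follow-up. Table 1 is captioned "with a power of 80% and $\alpha = 0.05$ under 1:1 matching ratio", its significance column is headed "sign.level one-sided", and the result is 34,585.4 observations per group (69,170.8 overall). Section 9.5 does not mention overlap. It says that analysis starts once a "sufficient sample size to exclude a HR of 1.5 with 80% power is reached", and that the meta-analysis of the MarketScan and Optum dual-therapy cohorts "will be the main analysis of this study as it will be the only powered analysis".

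Section 9.4 (Data sources) gives the purpose of pooling: "Meta-analysis of the 2 databases might be used, when appropriate, to achieve the required study size".

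Section 9.9.1 (Data source) states: "It is estimated that two databases (MarketScan and Optum CDM) have about 10-15% overlap". It adds that duplicates cannot be identified and removed, and that no effect on the results is expected "because it will be much smaller in the study population". It then describes a sensitivity analysis over several overlap scenarios (0%, 10%, 20% and so on), with the 95% confidence intervals of the primary outcome adjusted to match.

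Section 9.7.4 (Meta-analysis) says that a variance correction for duplicates will be used for the primary outcome. It defines rho as the percentage of overlapping observations in the smaller dataset and, because the true overlap is unknown, varies it in 10% steps. SAP section 10.4 only refers back to protocol 9.7.4.

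**The concern.** A person present in both databases, with the same drug and the same event, adds two observations to the count but only one person's information. Section 9.5 converts a count into 80% power as if every observation were independent. If the start condition is checked on the summed count of the two databases, duplicates help to meet it.

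The reassurance in 9.9.1 does not settle this. Restricting both databases to dual-therapy initiators reduces the number of duplicates, but does not by itself reduce their percentage, and the percentage is what enters the variance formula in 9.7.4. Other features of the selection could reduce the percentage, but 9.9.1 names none and gives no count.

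Two things are at stake. The first is the power stated for the only analysis the protocol calls powered. The second is the confidence interval that decides whether 1.5 is excluded: several overlap values are planned and none is designated, so its width is not fixed in advance.

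**Working it through.** **Inputs from protocol 9.5:** p1 = p2 = p = 0.0022; margin R = 1.5; one-sided alpha 0.05 (z = 1.645); power 80% (z = 0.842); 1:1; one year of follow-up for all.

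**Inputs from 9.9.1 and 9.7.4:** overlap of 10-15% between whole databases; rho is the overlapping share of the smaller dataset.

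**Assumptions, because the documents give no figure:** the overlap in the matched cohorts (2%, 5%, 10% and 15% shown), the split between databases (50:50 and 70:30 shown), and whether duplicates survive matching in both arms or mainly in the empagliflozin arm.

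**Step 1. Reproduce the stated size.** The test compares R·p1 − p2 with zero. The difference under the alternative is d = (1.5 − 1) × 0.0022 = 0.0011. The maximum likelihood rates restricted to p2 = 1.5·p1 are 0.00176 and 0.00264.

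- Null SD: s0 = √[1.5² × 0.00176 × (1 − 0.00176) + 0.00264 × (1 − 0.00264)] = 0.08115
- Alternative SD: s1 = √[(1.5² + 1) × 0.0022 × (1 − 0.0022)] = 0.08446
- n = [(1.645·s0 + 0.842·s1)/d]² = [(0.13348 + 0.07109)/0.0011]² ≈ 34,585.4 per group (evaluated unrounded)

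This matches Table 1 exactly.

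**Step 2. Variance factor from overlap.** Let the larger database hold share a of the observations and the smaller 1 − a. Section 9.7.4 adds a covariance term 2·w1·w2·rho·σ² to the pooled variance. Counting each duplicate as two fully correlated observations gives, relative to no overlap:

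- duplicates in both arms: V = 1 + 2(1 − a)·rho, which is 1 + rho at 50:50 and 1 + 0.6·rho at 70:30;
- duplicates in one of two equally informative arms: half the excess, V = 1 + (1 − a)·rho, which is 1 + 0.5·rho at 50:50 and 1 + 0.3·rho at 70:30.

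The printed definition of σ² in 9.7.4 cannot be used as it stands on the variance scale. A sample-size-weighted average was used in its place, and at 50:50 this gives the same factor 1 + rho.

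**Step 3. Power at 34,585 counted observations per group.** Power = Φ[(d·√(n/V) − 1.645·s0)/s1]. The size that restores 80% is n·V, and the standard error grows by √V.

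| Scenario | V | Effective n per group | Power | Size for 80% |
|---|---|---|---|---|
| No overlap | 1.00 | 34,585 | 80.0% | 34,585 |
| 2%, 50:50, both arms | 1.02 | 33,907 | 79.3% | 35,277 |
| 5%, 50:50, both arms | 1.05 | 32,938 | 78.3% | 36,315 |
| 10%, 50:50, both arms | 1.10 | 31,441 | 76.7% | 38,044 |
| 15%, 50:50, both arms | 1.15 | 30,074 | 75.1% | 39,773 |
| 10%, 70:30, both arms | 1.06 | 32,628 | 78.0% | 36,661 |
| 15%, 70:30, both arms | 1.09 | 31,730 | 77.0% | 37,698 |
| 10%, 50:50, empagliflozin only | 1.05 | 32,938 | 78.3% | 36,315 |
| 15%, 50:50, empagliflozin only | 1.075 | 32,173 | 77.5% | 37,179 |
| 10%, 70:30, empagliflozin only | 1.03 | 33,578 | 79.0% | 35,623 |
| 15%, 70:30, empagliflozin only | 1.045 | 33,096 | 78.5% | 36,142 |

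For 5-15% overlap at 50:50 in both arms, the standard error is √1.05 = 1.025 to √1.15 = 1.072 times its value at zero overlap.

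**Step 4. Which overlap value gives the main interval?** Section 9.7.4 says a correction will be used for the primary outcome, in 10% steps. Section 9.9.1 calls the same exercise a sensitivity analysis and lists 0% among the scenarios. Neither names a main value, and 15%, the top of the plan's own estimate, is not on the listed grid.

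**The case against.** The 10-15% describes whole databases, and 9.9.1 says the cohort figure will be much smaller. That is plausible. To be a duplicate in the analysis, a person must qualify separately in each database on six months' registration, a type 2 diabetes code and new use within the same treatment line, and must then survive 1:1 caliper matching within calendar quarter in each. The data cuts differ too. This argument stands, so power of 75-78% cannot be stated as fact: it holds only if the whole-database overlap carries over, and even then the milder 70:30, empagliflozin-only case lies above that range. The argument still supplies no number, and any non-zero overlap puts power at 34,585 below 80%.

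A reader might infer that the main confidence interval is computed at zero overlap and is therefore too narrow. The documents do not support that: 9.7.4 commits to a correction for the primary outcome, and 0% is only one listed scenario. What stands is that no value is designated. Correcting the variance at analysis also does not repair 9.5, because widening the interval is what lowers the power.

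Finally, 34,585 is a threshold. All eligible patients are included, and the matched count is not in these documents. If it is well above the threshold, power may exceed 80% despite overlap.

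A separate limit concerns the level. These figures use the plan's one-sided 0.05, while the planned intervals are 95%. On an upper 95% limit, the same formula gives about 70.5% even with no overlap.

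**Conclusion.** The concern holds in a conditional form. The stated 34,585.4 is correct for independent patients, but the plan fills it from two sources with duplicates it cannot remove. The unconditional 80% in 9.5 is therefore not delivered at that counted size for any non-zero overlap. The shortfall is under 2 points at an assumed 2-5% overlap, about 3 to 5 points at 10-15% with equal databases and duplicates in both arms, and about 1 to 3 points with a 70:30 split or duplicates in the empagliflozin arm only. The cohort overlap, the split and the matched count are all missing from the documents, so no single figure can be given. Separately, and whatever the true overlap, the value behind the main confidence interval is not specified in advance.

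**What to change.** - **Section 9.5:** state that 34,585 means independent patients per group, and replace the unconditional 80% with the power of the pooled analysis across 0-15% overlap (80.0% at 0%, 78.3% at 5%, 76.7% at 10% and 75.1% at 15% for equal databases and both arms), with the assumed database split stated.
- **Sections 9.7.4 and 9.9.1:** name in advance one non-zero overlap value for the main confidence interval, for example one within the plan's own 10-15% range unless a cohort-level estimate supports a lower one. Show 0% and the other values as sensitivity analyses, and use the same description in both sections.
- **Section 9.9.1:** support the expectation of a much smaller overlap with a count or an argument about the percentage, or delete it.

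The cost is wording in three sections, with no new patients or data. The downside is that stated power falls by about 1 to 5 points, and the main interval is up to about 7% wider (on the log scale) than at zero overlap.

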## **9.5 STUDY SIZE**

All patients with T2DM who newly initiate therapy with empagliflozin or study comparator who meet the inclusion and exclusion criteria will be included in the analysis.

Event rate of acute pancreatitis reported in patients with T2DM who are treated with canagliflozin was reported to be 2.2 per 1000 PY [\[RRA-21430\]](#). This rate was used for sample size calculation using the formula of Farrington and Manning (maximum likelihood method) [\[R14-3295\]](#).

Null hypothesis H0:  $\pi_2 / \pi_1 \geq 1.5$  (non-inferiority)

A single stage (fixed sample size) design was chosen.

For specified  $\alpha = 0.05$  and rates  $\pi_1 = 0.0022$  and  $\pi_2 = 0.0022$  (odds ratio of 1.000) the power (1 -  $\beta$ ) is 80.0% if the test stages consist of the sample sizes given in the last two columns of [Table 1](#).

The computation assumes an allocation ratio (n2/n1) = 1 (Table 1). It is assumed that all patients have 1 year of follow up.

**Table 1** Number of empagliflozin initiators and empagliflozin-exposed person-years needed to detect a HR of 1.5 and 2.0 with a power of 80% and  $\alpha = 0.05$  under 1:1 matching ratio

Hazard ratio (HR)	Information rate	Bunds accept $H_0$	Bunds reject $H_0$	sign.level one-sided	$\alpha$ spent	$\beta$ spent	power achieved	Observations per exposure group	Overall observations
1.5	1.0	1.645	1.645	0.0500	0.0500	-	0.8000	34585.4	69170.8

ADDPLAN Adaptive Design Software 2019 and SAS 9.4 software ( ) were used to calculate the sample size.

Analysis of this study will be initiated as soon as a sufficient sample size to exclude a HR of 1.5 with 80% power is reached. Based on a feasibility assessment conducted in Optum and MarketScan databases using data between 1 August 2014 and the latest data-cut available in MarketScan (30 September 2020) and Optum (31 March 2021), the dual-therapy cohort was reported with the highest number of empagliflozin initiators, therefore meta-analysis of the dual therapy cohorts including the data from the MarketScan and Optum databases will be the main analysis of this study as it will be the only powered analysis.

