Name of company: Boehringer Ingelheim						
Name of finished medicinal product: Jardiance®						
Name of active ingredient: A10BK03 Empagliflozin						
Protocol date: 10/DEC/2021	Study number: 1245-0201	Version/Revision: 1.0		Version/Revision date: NA		
Null hypothesis $H_0: \pi_2 / \pi_1 \geq 1.5$ (non-inferiority) A single stage (fixed sample size) design was chosen. For specified $\alpha = 0.05$ and rates $\pi_1 = 0.0022$ and $\pi_2 = 0.0022$ (odds ratio of 1.000) the power (1 - $\beta$ ) is 80.0% if the test stages consist of the sample sizes given in the last two columns of the table. The computation assumes an allocation ratio ( $n_2/n_1$ ) = 1. It is assumed that all patients have 1 year of follow up.						
Hazard ratio (HR)	sign. level one-sided	$\alpha$ spent	$\beta$ spent	power achieved	Observations per exposure group	Overall observations
1.5	0.0500	0.0500	-	0.8000	34585.4	69170.8
ADDPLAN Adaptive Design Software 2019 and SAS 9.4 software (██████████) were used to calculate the sample size. Analysis of this study will be initiated as soon as a sufficient sample size to exclude a HR of 1.5 with 80% power is reached. Based on a feasibility assessment conducted in Optum and MarketScan databases using data between 1 August 2014 and the latest data-cut available in MarketScan (30 September 2020) and Optum (31 March 2021), the dual-therapy cohort was reported with the highest number of empagliflozin initiators, therefore a meta-analysis of the dual therapy cohorts including the data from the MarketScan and Optum databases will be the main analysis of this study as it will be the only powered analysis.						

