

• Addition of or switch to an SGLT2i (in empagliflozin users, this would mean switch to a non-empagliflozin SGLT2i) (see section 9.7)

• Discontinuation of index drug

• End of study (date of death, date of end of registration in the database, or study end date).

 
As a first step, a propensity score (PS) will be estimated for each cohort member at the index date, based on the values of the observed covariates during the look-back period. In this study, propensity scores will be estimated by conducting multivariable logistic regression modelling and incorporating measured potential predictors of therapy as independent variables and exposure group status (empagliflozin group vs. comparator) as the outcome. We will use PS matching to balance a number of covariates. Key advantages of PS matching are that large numbers of covariates that can be adjusted for even when studying infrequent outcomes, the achieved covariate balance can be documented, multiple outcomes can be studied after a single matching process, [R13-1120] and patients who cannot find comparable pairs will be implicitly dropped out of the analysis increasing the validity of findings [R17-1404].
 
The propensity score will be used to match patients in a 1:1 ratio using a nearest-neighbor algorithm and calipers of width equal to 0.2 of the standard deviation of the logit of the propensity score [R13-3590, R18-2599, R16-1227]. A 1:n variable ratio matching will not be used as it involves several complications while providing only a minimal gain in estimation precision [R17-1267]. If balance is not achieved, the PS model will be refitted using interaction terms [R18-2599]. PS balance achievement will be inspected by tabulating all patient characteristics by treatment status and by assessing the standardized differences. Any patient characteristics with a standardized difference of >10% will be considered for additional post-matching adjustment [R13-3590].
 
To account for patient characteristics changing over time, patients will be matched on the calendar quarter-year of initiation of the study medication. If we lose too many patients using this method, we may instead decide to match on year of initiation of index medication and then include calendar quarter-year variable in the PS model.
 
The incidence rates (per 1000 PY) and corresponding 95% confidence intervals (CI) of acute pancreatitis during the follow-up time will be calculated in each exposure group of interest in the unmatched and PS-matched cohorts.
			

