
Name of company:			
Boehringer Ingelheim			
Name of finished medicinal product:			
Jardiance®			
Name of active ingredient:			
A10BK03 Empagliflozin			
Protocol date:	Study number:	Version/Revision:	Version/Revision date:
10/DEC/2021	1245-0201	1.0	NA
	
Cox proportional hazards regression models based on time-to first acute pancreatitis event will be used to estimate hazard ratios (HR) and 95% CIs for each treatment line comparison of interest in the unmatched and PS-matched cohorts. Based on a feasibility assessment conducted in Optum and MarketScan databases using data between 1 August 2014 and the latest data-cut available in MarketScan (30 September 2020) and Optum (31 March 2021), meta-analysis of the dual therapy cohorts including the data from the Marketscan MarketScan and Optum databases will be the main analysis of this study:
 

• Dual therapy: Empagliflozin vs. SU (both on a background of metformin)

 
All results will be presented for each database separately but if there is not enough sample size in each treatment line cohort in each database, after evaluating potential heterogeneity, meta-analysis techniques will be used to pool the treatment line cohorts of the 2 databases. Descriptive tables and all parameter estimates from the main and all sensitivity analyses will be pooled using meta-analytic methods assuming a fixed effects model, to avoid potential biases associated with random effects pooling in the context of few databases [R17-1410].
		
Milestones:	
The study period is between 1 August 2014 (start of data collection) and the latest data-cut available in Marketscan (30 September 2020) and Optum (31 March 2021) (end of data collection). In this multi database study, the start of data analysis will be in December 2021 and the final report will be available in Q3 2022.
		

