For patients who add an incretin-based therapy, SGLT2i, or a within treatment line comparator index drug, their data will be censored on the date of the prescription claim for the added medication.

Patients with chronic use of insulin at baseline (see SEAP for definition) in the outpatient setting during the follow-up period will be censored from the study.

From a feasibility assessment conducted in November 2021, it is known that there are not enough study participants in the Optum and MarketScan database in each therapy line and the dual-therapy cohort was reported with the highest number of empagliflozin initiators. Therefore, a meta-analysis of the dual therapy cohorts including the data from the Marketscan MarketScan and Optum databases will be the main analysis of this study

Meta-analysis of different treatment line cohorts with the different comparators (first, second and third line) will not be conducted in this study as patients in these 3 cohorts will likely have very different profiles including different disease stages, and results would be difficult to interpret.

The incidence rates (per 1000 PY) and corresponding 95% confidence intervals (CI) of acute pancreatitis during the follow-up time will be calculated in each exposure group of interest in the unmatched and PS-matched cohorts.

All results will be presented for each database separately but if there is not enough sample size in each treatment line cohort in each database, after evaluating potential heterogeneity, meta-analysis techniques will be used to pool the 2 treatment line cohorts of the 2 databases. Descriptive tables and all parameter estimates from the main and all sensitivity analyses will be pooled using meta-analytic methods assuming a fixed effects model, to avoid potential biases associated with random effects pooling in the context of few databases [R17-1410].

Cox proportional hazards regression models based on time-to first acute pancreatitis event will be used to estimate hazard ratios (HR) and 95% CIs for each treatment line comparison of interest (in each database or in case of limited sample size a meta-analysis of 2 databases) in the unmatched and PS-matched cohorts. Proportionality hazard assumption will be checked using the log rank test.

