#### 9.7.4 Meta-analysis

After evaluating potential treatment effect heterogeneity we may pool results from the two databases. Descriptive tables and all parameter estimates from the main and all sensitivity analyses will be pooled using meta-analytic methods assuming a fixed effects model, since random effects pooling can be biased in the context of few databases [R17-1410]. Calculation of an overall mean/proportion/hazard ratio from two databases reporting a single mean/proportion/hazard ratio will use the inverse variance method for pooling [R02-0971].

To correct variance for potential duplicates in pooling two databases for the primary outcome, the following method will be used. The variance correction for overlapping samples when pooling multiple databases was described by [REDACTED] and [REDACTED] [M20-0016].

[figure not shown]
The formula for the variance is given by

$$\hat{\sigma}_{combined}^2 = w_1^2 \hat{\sigma}_1^2 + w_2^2 \hat{\sigma}_2^2 + 2w_1 w_2 \rho \hat{\sigma}^2$$

Where

- $w_1$  and  $w_2$  are the weights applied to the two databases and  $w_2 = 1 - w_1$
- $\hat{\sigma}_1^2$  and  $\hat{\sigma}_2^2$  are the variance estimates from both databases
- $\rho$  is the % of overlapping observations in the smaller dataset
- $\hat{\sigma}^2 = (n_1 \hat{\sigma}_1^2 + n_2 \hat{\sigma}_2^2) / 2$  where  $n_1$  and  $n_2$  are the number of observations in both databases

Given that an exact overlap is not known between databases, estimates in 10% intervals will be used to assess varying degrees of variance in the pooled point estimates. The pooled analyses will be conducted using R package **rmeta** in R studio [R20-1986, M20-0016].

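### The study is sized on a one-sided 0.05 test of HR 1.5, but the visible analysis text plans only 95% intervals; if the 95% limit decides, power is about 70%, not 80%

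*Protocol*

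**What the plan says.** **Sizing.** Protocol 9.5 and the abstract state a non-inferiority null hypothesis (ratio of 1.5 or more), with equal rates of 0.0022 assumed in both groups, 1:1 allocation and one year of follow-up per patient. In the abstract's table the column headed "sign. level one-sided" shows 0.0500. Table 1 in 9.5 adds a rejection bound of 1.645, 80% power and 34,585.4 per group (69,170.8 overall). Section 9.5 then makes the start of the analysis depend on when "a sufficient sample size to exclude a HR of 1.5 with 80% power is reached". It names the pooled dual-therapy comparison as the only powered analysis.

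**Analysis.** Protocol 9.7.3 says: "Cox proportional hazards regression models based on time-to first acute pancreatitis event will be used to estimate hazard ratios (HR) and 95% CIs". The abstract likewise plans "95% CIs for each treatment line comparison of interest in the unmatched and PS-matched cohorts". SAP 10.3 and 10.4 only point back to protocol 9.7.3 and 9.7.4. None of these sections mentions 1.5, a 90% interval or a one-sided bound. ENCePP checklist item 2.1.4, which asks which hypotheses will be tested, is marked not applicable.

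**Overlap.** Protocol 9.7.4 says: "To correct variance for potential duplicates in pooling two databases for the primary outcome, the following method will be used". Because the true overlap is unknown, "estimates in 10% intervals will be used to assess varying degrees of variance in the pooled point estimates". Section 9.9.1 says that the databases "have about 10-15% overlap", expects much less in the study population, and describes the overlap scenarios (0%, 10%, 20% and so on) as a sensitivity analysis with adjusted 95% intervals.

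**The concern.** Excluding a hazard ratio of 1.5 is the stated purpose of the study size. A reader of the results will look for that conclusion in the interval that is reported, and the only interval level in the visible analysis text is 95%. Its upper limit corresponds to one-sided 0.025, a stricter criterion than the one used for sizing, so the stated 80% does not describe the chance of meeting it.

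What is at stake is narrow. The cohort, the estimate and the reported 95% interval stay the same whichever limit is used. Only the statement that 1.5 has, or has not, been excluded depends on the choice. If that choice is open when the results are known, a result in the band where the limits differ could be described either way.

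**Working it through.** **Inputs** (protocol 9.5): p1 = p2 = 0.0022; margin R = 1.5; 1:1 allocation; one-sided 0.05; power 0.80; one year each; Farrington-Manning maximum-likelihood formula.

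**1. Reproduce the plan's figure.** The rates constrained to a ratio of 1.5 are q1 = 0.001760 and q2 = 0.002640.

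- Null variance: v0 = q2(1 − q2) + R²·q1(1 − q1) = 0.006585, square root 0.08115.
- Alternative variance: v1 = p(1 − p)(1 + R²) = 0.0022 × 0.9978 × 3.25 = 0.007134, square root 0.08446.
- Distance: d = R·p1 − p2 = 0.0011.
- n = (z(1−α)·√v0 + z(0.80)·√v1)² / d² = (1.645 × 0.08115 + 0.842 × 0.08446)² / 0.0011² = 34,585.4 per group (computed with unrounded values).

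This matches Table 1 exactly. Expected events: 2 × 34,585.4 × 0.0022 = 152.2.

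**2. Same size, 95% upper limit (one-sided 0.025).** Power = Φ[(d·√n − 1.960·√v0) / √v1] = Φ[(0.20457 − 0.15905) / 0.08446] = Φ(0.539) = 70.5%.

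**3. Size needed for 80% with the 95% limit.** n = (1.960 × 0.08115 + 0.842 × 0.08446)² / 0.0011² = 43,772 per group. That is 2 × 43,772 × 0.0022 = 192.6 events, and 43,772 / 34,585.4 = 1.27 times the stated size.

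**4. Cross-check on the log hazard ratio scale.** SE = √(4 / 152.2) = 0.162 and ln 1.5 = 0.405.

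| Deciding limit | Power, true HR 1.0 | Largest observed HR that excludes 1.5 |
|---|---|---|
| 90% upper | Φ(0.405/0.162 − 1.645) = 80.4% | 1.5·exp(−1.645 × 0.162) = 1.15 |
| 95% upper | Φ(0.405/0.162 − 1.960) = 70.6% | 1.5·exp(−1.960 × 0.162) = 1.09 |

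The limits therefore differ only for observed hazard ratios between about 1.09 and 1.15. At a true HR of 1.0 this happens in 80.4% − 70.6% = 9.8% of studies, or about one in ten.

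**5. Overlap, by comparing the text.** Section 9.7.4 presents the variance correction as something that will be applied to the primary outcome. Section 9.9.1 presents the overlap scenarios as sensitivity analysis, with 0% among them. Neither says at which overlap level a limit would be compared with 1.5. For any overlap above zero the added term 2·w1·w2·ρ·σ² is positive, so the limit widens and power falls on either reading. No figure is given for this loss. It would need an assumed split between the databases and a reading of σ² as a weighted average, which is not how 9.7.4 prints it.

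**The case against.** The strongest reply is that a rule exists. Section 9.5 gives the null hypothesis, the one-sided level and the 1.645 bound, and together these are equivalent to the 90% upper limit. On that view 9.7.3 lacks only a cross-reference. This stands in part: it would be wrong to say that the protocol contains no test of 1.5. But the test appears only as the basis of a binomial size calculation with one year per patient. The planned inference is a pooled as-treated Cox hazard ratio, and nothing visible transfers the bound to it. The checklist answer points away from a test.

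Second, the objectives speak of comparing risk or incidence rates, all eligible patients are included and the data cuts are fixed. The figure of 1.5 can therefore be read as a precision target. That is a fair reading, but then the 80% is a planning figure and should not be cited beside a conclusion drawn from the 95% interval.

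Third, protocol 9.7.5 and SAP 10.5 do not appear in the public text and may hold the rule. This stands, and it limits confidence. If the rule is there, a cross-reference is enough.

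A reader might also infer more than the documents support:

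- **That Table 1 is wrong.** It is not; it reproduces exactly.
- **That a 95% interval contradicts a one-sided 0.05 size calculation.** It does not. Estimating at 95% beside such a test is ordinary practice.
- **That the study has only 70% power.** That figure holds only if the 95% limit is the criterion, and no passage says so.
- **That the main analysis leaves several intervals of equal standing because of overlap.** Section 9.9.1 calls those scenarios a sensitivity analysis, so the issue is a tension in wording with 9.7.4.

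**Conclusion.** The point holds as a gap between the sizing test and the planned inference, and it should be fixed. The study size is right for the test in 9.5. That test is not carried into the visible analysis sections, and if the planned 95% upper limit is used to exclude 1.5, power at 34,585 per group is about 70% (70.5% by the plan's own formula, 70.6% on the log hazard ratio scale).

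The practical effect is limited to observed hazard ratios of about 1.09 to 1.15. These figures assume a rate of 0.0022 in both groups, one year of follow-up each, a true hazard ratio of 1.0 and no overlap between the databases. Confidence is moderate because of the two sections that cannot be seen.

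**What to change.** Before results are seen, state one rule in protocol 9.7.3 and SAP 10.3:

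- **(a)** HR 1.5 is excluded when the upper limit of the pooled two-sided 90% interval is below 1.5. This carries over the test in 9.5 and keeps the 80%; the 95% interval remains for estimation. Or
- **(b)** the 95% upper limit decides, and the power in 9.5 and the abstract is restated as about 70% at the stated size.

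In either case, reconcile 9.7.4 with 9.9.1 by naming the one overlap level at which the deciding limit is read, and report the other levels as sensitivity results. Bring the answer to checklist item 2.1.4 into line with the choice.

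Optional: follow-up is as-treated and not fixed at one year, so the size that triggers the analysis could be expressed as matched person-years (34,585.4 × 2 × 1 year, about 69,171) or as pooled events (about 152). Actual follow-up is not given, so this could move power in either direction.

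The cost is wording only, with no new data and no re-sizing. Option (b) makes the stated power less favourable.
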